9.4 Analysis of the primary variable(s)

The purpose of this study is to characterize the dose response relationship among VAY736 doses (5, 50, 300 mg s.c. every 4 weeks) and placebo with regards to the change from baseline in ESSDAI at week 24 using all ESSDAI data collected during the 24 weeks of treatment during period 2. The goals of the study are:

- to confirm an overall dose-response signal, and
- to estimate the optimum dose that corresponds to the clinically relevant effect (i.e., 3-point change in ESSDAI) over placebo.

The generalized MCP-Mod methodology ([Bretz et al., 2005](#); [Pinheiro et al., 2014](#)) will be used to address these goals. Testing will be done at one-sided 5% alpha level.

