9.4.1 Variable(s)

The primary variable is the change from baseline in ESSDAI (12-domain score) over 24 weeks. This will be defined as the baseline ESSDAI minus the post-baseline ESSDAI value thus positive values will indicate improvement in disease status. The time point of primary interest is week 24 at which the dose-response will be evaluated.

The primary analysis will be based on the FAS.

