## 2.5 Analysis of the primary objective

### 2.5.1 Primary endpoint

The following estimand framework is adopted for the primary analysis.

- Population: FAS
- Variable of interest: Change from baseline in ESSDAI total score after 24 weeks of VAY736 or placebo administration every four weeks. This will be defined as the Week 24 ESSDAI value minus the baseline ESSDAI value with negative values indicating improvement in disease status.
- Intercurrent events: Regardless whether early termination from the study, interruption of study treatment, or intensified concomitant treatment (local and systemic) has occurred.
- Summary measure: Adjusted mean change from baseline in ESSDAI total score at Week 24 will be calculated from MMRM.

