#### 5.4.1.1 Repeated measures analysis

As a first step in the dose-response characterization a repeated measures model will be fitted to the changes from baseline in ESSDAI up to week 24. The change from baseline in ESSDAI is assumed to be normally distributed.

An MMRM model will be fitted to the changes from baseline in ESSDAI including all time points until week 24 including the following fixed factors

- treatment group
- (analysis) visit
- treatment group by visit interaction
- stratification factor baseline ESSDAI score  $<10$  or  $\geq 10$
- geographic region

as well as baseline ESSDAI as a continuous covariate. An unstructured variance-covariance matrix will be fitted to model the dependency between repeated observations. Graphical checks on the model assumptions of normality of the data will be provided.

The mean treatment effects will be estimated at week 24. Together with the estimated covariance matrix, they will be used in the dose-response modeling as described below.

[figure not shown]
To allow adjustment for correlations between time points within patients, this MMRM approach is adopted to obtain the least squares means (LSM) fits.

The mean responses at each individual dose will be obtained through covariate-adjusted treatment effects by modeling the primary efficacy variable using a mixed-effect model for repeated measures (MMRM). The model will contain terms (factors) given above. Treatment group, visit, and geographical region will be fitted as categorical variables and baseline score as a continuous covariate. The model will be fitted using the SAS procedure “PROC MIXED”. Unstructured covariance matrix will be used (TYPE = UN), thus allowing adjustment for correlations between time points within patients. In order to get the variance covariance matrix of treatment effects to be full rank matrix, no intercept option will be used (NOINT option in MODEL statement). Adjusted means and the corresponding variance covariance matrix will be estimated. The estimated treatment differences for all treatment comparisons will be tabulated along with the associated 90% confidence intervals (ALPHA = 0.1) and two-sided p-values. No adjustment for multiplicity will be made. The estimated treatment means along with 90% CIs will be presented graphically as well. For calculation of denominator degrees of freedom Kenwood-Rogers method would be used (DDFM=KR)

In case the MMRM model does not converge the following sequential steps will be used:

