1. change ddfm=kr to ddfm=bw. If still no convergence, perform step 2.

2. change type=un to type=cs. If still no convergence, perform step 3.
3. remove covariates in the following order until convergence: geographic region, stratification factor, treatment group by visit interaction.

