#### 5.4.2 Secondary analysis

See [Section 2.6.2](#).

In case the MMRM model does not converge the following sequential steps will be used:

1. change ddfm=kr to ddfm=bw. If still no convergence, perform step 2.
2. change type=un to type=cs. If still no convergence, perform step 3.
3. remove covariates in the following order until convergence:, geographic region, stratification factor, treatment group by visit interaction.

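### The last non-convergence step in the SAP drops treatment-by-visit, so the reported week-24 effect would become an average over weeks 4 to 24

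*SAP*

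**What the plan says.** The primary model in SAP 5.4.1.1 is an MMRM for change in ESSDAI at weeks 4, 8, 12, 16, 20 and 24. It has treatment, visit, treatment-by-visit, ESSDAI stratum, region and baseline ESSDAI, with an unstructured covariance matrix (UN) and Kenward-Roger degrees of freedom. On its output the SAP says: "The mean treatment effects will be estimated at week 24". It continues: "Together with the estimated covariance matrix, they will be used in the dose-response modeling as described below".

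If the model does not converge, three steps follow in order:

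1. Kenward-Roger is replaced by between-within degrees of freedom.
2. "change type=un to type=cs. If still no convergence, perform step 3" (UN to compound symmetry, CS).
3. "remove covariates in the following order until convergence: geographic region, stratification factor, treatment group by visit interaction".

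SAP 5.4.2 gives the same steps for the secondary MMRMs, ending: "remove covariates in the following order until convergence:, geographic region, stratification factor, treatment group by visit interaction".

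The target is stated elsewhere. Protocol 9.4.1: "The time point of primary interest is week 24 at which the dose-response will be evaluated". SAP 2.5.1: "Adjusted mean change from baseline in ESSDAI total score at Week 24 will be calculated from MMRM". One of the two goals in Protocol 9.4 is "to estimate the optimum dose that corresponds to the clinically relevant effect (i.e., 3-point change in ESSDAI) over placebo". For the secondary variables, Protocol 9.5.1 promises estimates by dose and by visit, and SAP 1.2 lists separate endpoints at weeks 4, 8, 12 and 16.

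No step names an empirical variance estimator. No visible text says how a week-24 effect would be obtained once the interaction is gone.

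**The concern.** The removal list treats treatment-by-visit as one more covariate. Region and stratum are adjustment terms, and dropping them leaves the question unchanged. The interaction is what allows the week-24 effect to differ from the week-4 effect. Removing it lets a computing problem change the estimand, and it does so just before the estimates enter a dose-response model whose purpose is to find a dose for a 3-point effect over placebo at week 24. For the secondary variables it also removes the visit-specific comparisons that the objectives require.

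The step before it, UN to CS, is more likely to be reached. It keeps the week-24 target but assumes one variance for all visits and one correlation for all pairs of visits. With no empirical estimator named, the default is the model-based covariance matrix, and that matrix goes to the dose-response step. This affects every endpoint given the MCP-Mod analysis: ESSDAI, ESSPRI and FACIT-F (SAP 2.6.2), and the ESSPRI subscores added in the July 2019 entry of the SAP document history.

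**Working it through.** The plan gives no figure to reproduce here. The visible text has no SD, visit correlation, dropout rate or time course, so all of these are assumed below. From the documents come the six visits, about 45 patients per arm, the one-sided 5% level and the 3-point effect. Effects are written as benefit over placebo in ESSDAI points.

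**Interaction removed.** Let d(v) be the true treatment difference at visit v. With complete data and CS, every visit has equal weight, so the single treatment term estimates the mean of the six d(v). Means can still be printed for week 24, but their difference is this average.

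| Assumed d at weeks 4, 8, 12, 16, 20, 24 | True week 24 | Reported |
|---|---|---|
| 0.5, 1, 1.5, 2, 2.5, 3 (linear) | 3.0 | 10.5/6 = 1.75 |
| 0, 0, 0.5, 1, 2, 3 (late) | 3.0 | 6.5/6 = 1.08 |
| 3, 4, 4.5, 4, 3.5, 3 (early peak) | 3.0 | 22/6 = 3.67 |
| 3 at every visit | 3.0 | 18/6 = 3.00 |
| 2, 3, 4, 3, 3, 3 | 3.0 | 18/6 = 3.00 |
| 1, 2, 3, 2, 1, 0 (transient) | 0.0 | 9/6 = 1.50 |

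Dropout shifts weight to the earlier visits. In simulation with 16-21% missing at week 24 (missing at random), the linear case gave 1.59-1.65 and the late case 0.92-0.99. With CS and the interaction kept, the linear case gave 2.97-3.04.

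**CS with the interaction kept.** With complete data the week-24 estimate is the same as under UN. The CS model-based variance uses the mean of the six visit variances; the true variance uses the week-24 variance. So

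ratio r = sqrt(mean visit variance / week-24 variance), and one-sided size = 1 - Phi(1.645 r).

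Example, SD rising linearly from 2.5 to 5: mean variance = 88.75/6 = 14.79; r = sqrt(14.79/25) = 0.769; size = 1 - Phi(1.265) = 10.3%.

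| SD, week 4 to week 24 | r | Size |
|---|---|---|
| 2.5 to 5 | 0.769 | 10.3% |
| 3 to 5 | 0.812 | 9.1% |
| 4 to 5 | 0.903 | 6.9% |
| constant | 1.000 | 5.0% |
| 5 to 4 | 1.128 | 3.2% |
| 5 to 3 | 1.353 | 1.3% |

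**Sandwich errors.** A simulation used four arms of 45, correlation 0.8 to the power of the lag, dropout depending on the previous value, and 3,000 null replicates (Monte Carlo error about 0.4-0.5 points). For SD 3 to 5, constant, and 5 to 4, the size was 9.2%, 5.8% and 4.3% with model-based CS errors, and 5.3%, 5.3% and 5.4% with sandwich errors.

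**The case against.** **The interaction step is nearly unreachable.** Five fits must fail first: UN with each degrees-of-freedom method, CS, CS without region, and CS without region and stratum. CS has two covariance parameters, against 6 x 7 / 2 = 21 for UN. This stands, and it sets the severity. It does not defend the rule, because a fallback list is written for the case in which it is used.

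**The CS half argues from silence.** Also true. The documents do not contradict themselves there; they only name no empirical estimator. The harm depends on the assumed SD path and is nil for a constant SD with complete data. In simulation, sandwich errors gave a clear gain only when the SD rose over time; the constant-SD difference (5.8% against 5.3%) is about one Monte Carlo error.

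**The sizes are not this trial's error rates.** A reader might infer from 10.3% that the primary test runs at twice its nominal level. The documents do not support that. The planned analysis uses UN; the figures are for one contrast, not the MCP-Mod test, whose candidate models are not visible; and the simulated data sets were not selected for UN failure. Weighted by an assumed trigger probability independent of the test statistic, even the worst case is small: 5% + 0.01 x 5.29 = 5.05% at a 1% trigger, and 5% + 0.05 x 5.29 = 5.26% at 5%.

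**Redaction.** Parts of SAP 2.5 and the dose-response text cannot be read. The fallback lists are visible and complete in both sections, and the dose-response step takes the MMRM output as its input.

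**Conclusion.** The interaction point holds and needs no numerical assumption: a model without treatment-by-visit cannot deliver the week-24 effect required by Protocol 9.4.1, SAP 2.5.1 and SAP 5.4.1.1 itself, nor the by-visit results promised for the secondary variables. The size of the discrepancy does rest on assumed time profiles: 1.08 to 3.67 for a true 3.0 in the cases shown. A reader might infer that the fallback always dilutes the effect. It does not: it can dilute it, exaggerate it, produce one where week 24 has none, or leave it unchanged.

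The CS point is a worthwhile improvement, not an error in the plan. Its direction and size cannot be known from the documents: about 1% to 10% single-contrast size over the assumed SD paths.

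Both are conditional on non-convergence. Severity: minor.

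**What to change.** In SAP 5.4.1.1 and 5.4.2, delete treatment-by-visit from the removal list and state that treatment, visit and their interaction are kept at every step. If a further step is wanted after region and stratum are removed, keep an all-visit model with the interaction and simplify other terms or the covariance.

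A week-24-only ANCOVA is a tempting last step but should be avoided. It would depart from Protocol 9.4 (use of all ESSDAI data over the 24 weeks), Protocol 9.4.3 (patients with missing post-dose time points stay in the analysis) and the MMRM summary measure in SAP 2.5.1.

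As a secondary change, where the sequence moves from UN to CS, base the standard errors and the covariance matrix passed to MCP-Mod on the empirical (sandwich) estimator, with the between-within degrees of freedom already set at step 1. Trying structures with visit-specific variances before CS is optional.

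The cost is a short edit in each of the two sections and one variance option in the code. Sandwich errors are slightly less stable at about 45 per arm. They correct the standard error, not any bias in the estimate from a wrong covariance structure under dropout.

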#### 5.4.2 Secondary analysis

See [Section 2.6.2](#).

In case the MMRM model does not converge the following sequential steps will be used:

1. change ddfm=kr to ddfm=bw. If still no convergence, perform step 2.
2. change type=un to type=cs. If still no convergence, perform step 3.
3. remove covariates in the following order until convergence:, geographic region, stratification factor, treatment group by visit interaction.

#### 5.5 Rule of exclusion criteria of analysis sets

**Table 5-4 Protocol deviations that cause subjects to be excluded from PP analysis**

Deviation ID	Description of Deviation
INCL03 & INCL06	No histology biopsy and negative serology at screening for [REDACTED]
INCL04	ESSDAI value <6 at screening, based on weighted scores of the 7 domains: biologic, hematologic, articular, cutaneous, glandular, lymphadenopathy and constitutional domains
INCL05	ESSPRI value <5 at baseline
TRT01	Patient did not receive at least one dose of study medication
TRT02	Patient received wrong study medication
TRT03	Patient missed two consecutive doses of study medication
CONC01	Use of other investigational drugs within 5 half-lives of enrollment or within 30 days whichever is longer, or longer if required by local regulations

[figure not shown]
Deviation ID	Description of Deviation
CONC02	Prior use of any B-cell depleting therapy (e.g., rituximab or other anti-CD20 mAb, anti-CD22 mAb or anti-CD52 mAb) 

• within 1 year prior to randomization

• or as long as B-cell count <50 cells/<math>\mu</math>L

CONC03	Prior treatment with any of the following within 180 days prior to randomization [REDACTED] CTLA4-Fc Ig (abatacept); anti-TNF- $\alpha$ mAb; intravenous/subcutaneous Ig; plasmapheresis; i.v. or oral cyclophosphamide; oral cyclosporine 

• Patients taking either hydroxychloroquine or methotrexate or azathioprine at consistent dose for <math>\geq</math>3 months prior to randomization are eligible if dose is maintained throughout the study

• If azathioprine is discontinued prior to enrollment, a minimum washout period of 30 days prior to randomization is required.

## 5.6 Steroids Conversion

**Table 5-5 Steroids conversion factors**

WHO drug code	Preferred term corticosteroid	Equivalent dose (mg)	Conversion factor
000447xx	Prednisone	5	1
000162xx	Prednisolone	5	1
000496xx	Methylprednisolone	4	1.25
012428xx	Meprednisone	4	1.25
001867xx	Prednylidene	5 5/7	0.875
000319xx	Triamcinolone	4	1.25
000146xx	Cortisone	25	0.2
000286xx	Hydrocortisone	20	0.25
002131xx	Fludrocortisone	2	2.5
000085xx	Betamethasone	0.75	6 2/3
000664xx	Paramethasone	2	2.5
000160xx	Dexamethasone	0.75	6 2/3
008827xx	Deflazacort	6	5/6
006445xx	Cloprednol	3	1 2/3

